14.4.1 Continuous endpoint

```
*** Analyze the continuous data on the last timepoint by ANCOVA ***;
PROC MIXED data=dsetall;
BY IMPUTATION ;
CLASS TRT;
MODEL CHG=BASELINE TRT;
LSMEANS TRT / PDIFF CL;
ESTIMATE "High vs Control" TRT 1 0 -1;
ESTIMATE "Low vs Control" TRT 0 1 -1;
         ODS OUTPUT LSMEANS=LSMEAN;
         ODS OUTPUT ESTIMATES=LSEST;
RUN;
*** Use Rubin's Rule ***;
PROC MIANALYZE parms=lsest;
BY LABEL;
MODELEFFECTS ALLEST;
ODS OUTPUT PARAMETERESTIMATES=PARMS;
RUN:
```

14.4.2 Binary endpoint

/*** compute the proportion difference and the corresponding standard error between the treatment groups (i.e. high dose vs. placebo, low dose vs. placebo) for each imputed dataset. Use Rubin's Rule to combine the results ***/

```
PROC MIANALYZE data=propest;
modeleffects prop_diff;
stderr se_diff;
ods output parameterestimates = PARMS;
run;
```

14.5 Appendix 5: Linear Mixed Model for Study Eye vs Fellow Eye Comparison – Sample SAS Code

PROC MIXED DATA=dset; /* assumes data presented in rows */ CLASS trt eye subject; /* be careful of the sequences of the variable here */ /* see notes later */ MODEL var_chg= eye trt eye*trt var bl/ DDFM=KENWARDROGER; REPEATED eye / SUBJECT=subject TYPE=UN R RCORR RI; LSMEANS eye*trt; ESTIMATE 'high dose: study eye vs fellow eye' eye 1 -1 eye*trt 1 -1 0 0 0 0; ESTIMATE 'low dose: study eye vs fellow eye' eye 1 -1 eye*trt 0 0 1 -1 0 0; ESTIMATE 'control: study eye vs fellow eye' eye 1 -1 eye*trt 0 0 0 0 1 -1; /* the variable 'eye' indicates whether the data are study eye or fellow eye */ /* 1 is associated to the study eye data */ /* -1 is associated to the fellow eye data */ /* treatment is coded as 1-high dose, 2-low dose, 0-control */ /* note the sequence of variables in the CLASS statement is very tricky */ $/\star$ in order for the ESTIMATE statement to work correctly: /* if it appears in CLASS statement as 'eye trt subject', then the ESTIMATE */ */ /* statement has to be, for example, /* ESTIMATE 'high dose:study eye vs fellow eye' eye 1 -1 eye*trt 1 0 0 -1 0 0; */ /* When interaction term is added, this statement must be modified

RUN;

*/

*/

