5 GENERAL ASPECTS FOR STATISTICAL ANALYSIS

5.1 General Methods

All analyses and summaries will be produced using SAS® version 9.4 (or higher).

For descriptive summary statistics, the efficacy and safety data will be summarized and displayed by treatment groups (Control, Low Dose, High Dose) and visits (Baseline, Month 1, 4, 8, 12, and End of Study).

Summary statistics will be presented for continuous variables, by way of number of subjects, mean, standard deviation (SD), median, first and third quartiles (Q1 and Q3, respectively), 5th and 95th percentiles (P05 and P95, respectively), minimum and maximum. Where specified, the 95% Confidence Interval (CI) of the mean will be calculated. Summary statistics will be presented where appropriate by treatment and nominal visit with an additional entry for the end of study.

For categorical variables (including binary variables), counts and percentages will be presented. Where specified, the 95% 2-sided CI for proportions will be calculated.

The listings, except the listing for screen failures, will include all randomized subjects in the database. In general, the subject listings will be sorted by treatment group, subject number, eye (starting with the study eye) and assessment date (and time, if applicable).

Data for unscheduled assessments will be included when calculating baseline values, selecting worst result for shift analyses, and for summary of normal/abnormal values. The safety summary of observed and change from baseline data will be performed by nominal (i.e., scheduled) visits. Unscheduled visits will be included in the analysis of End of Study, i.e., the last available non-missing treatment endpoint.

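### SAP Appendix 5's study-eye versus fellow-eye contrasts pick the wrong arms under the treatment coding it states; treatment coding in Appendices 4 and 7 is unstated or inconsistent

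*SAP*

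**What the plan says.** SAP 10.2 plans a supportive linear mixed model comparing study and fellow eyes on change in BCVA at Month 12, the first key secondary endpoint, and refers the reader to Appendix 5 for code. SAP 5.1 fixes the software: "All analyses and summaries will be produced using SAS® version 9.4 (or higher".

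The Appendix 5 code opens with "PROC MIXED DATA=dset", with no option for level order, and continues with "CLASS trt eye subject". A comment gives the coding: "treatment is coded as 1-high dose, 2-low dose, 0-control". The contrast for high dose is "ESTIMATE 'high dose: study eye vs fellow eye' eye 1 -1 eye*trt 1 -1 0 0 0 0". The low-dose row has the same form, with the pair `1 -1` moved to the third and fourth interaction positions; the control row has the pair in the fifth and sixth.

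Another comment warns that the sequence of variables in the CLASS statement matters. For the reversed sequence (eye before treatment) it offers `1 0 0 -1 0 0` as the high-dose interaction vector.

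Appendix 4 (multiple imputation under MAR, called by SAP 5.5) and Appendix 7 (control-based imputation, called by SAP 10.4.3) both use "ESTIMATE 'High vs Control' TRT 1 0 -1" and a matching low-dose row, `TRT 0 1 -1`. Appendix 4 states no treatment coding. Appendix 7 selects records with the character values `Active` and `Placebo`.

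**The concern.** The Appendix 5 contrasts are written as if the arms came in the order high, low, control. Its own coding puts control first. The warning in the code covers the order of the variables but not the order of the levels within treatment, so a programmer who follows it with care still gets the wrong arm.

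If the code were used as it stands, the untreated arm's difference between eyes would be printed as the high-dose result, and the high-dose result as low dose. That could hide a within-patient effect or suggest one that is not there, on an analysis meant to support a key secondary endpoint.

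**Working it through.** The plan gives no numerical figure to reproduce here. The check is whether each labelled row returns the arm that it names.

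**Inputs.** From Appendix 5: coding 0 = control, 1 = high, 2 = low; CLASS order treatment, eye, subject; no level-order option; the three vectors above. From SAP 5.1: SAS 9.4 or higher. Assumptions: SAS default ordering (sorted levels, last-listed CLASS variable changing fastest) and study eye as the first eye level.

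**Column order.** The sorted treatment levels are 0, 1, 2, that is control, high, low. Eye changes fastest, so the six interaction columns are control-study, control-fellow, high-study, high-fellow, low-study, low-fellow. The vector in the comment for the reversed CLASS order implies the same rule about which variable changes fastest.

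**Formula.** With eye effects e and interaction effects g, a row with `eye 1 -1` and `1 -1` in the pair for the k-th treatment level gives

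(e₁ − e₂) + (g_k1 − g_k2) = study minus fellow in the k-th level.

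**Numbers.** Take study-minus-fellow effects of control 0, high 10 and low 4 letters. These are illustrative assumptions and are not in the documents. Fitting the over-parameterised model and applying each vector gives:

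| Row label | Interaction vector | Arm picked | Returned | Should be |
|---|---|---|---|---|
| high dose | `1 -1 0 0 0 0` | control | 0 | 10 |
| low dose | `0 0 1 -1 0 0` | high | 10 | 4 |
| control | `0 0 0 0 1 -1` | low | 4 | 0 |

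All three rows are estimable, so SAS would print them without a warning.

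**Other level orders.** Alphabetical labels Control/High/Low give the same mislabelling. Descending codes (low, high, control) swap the two doses. An order of high, control, low gets only the high-dose row right. Of the orders tried, only high, low, control makes all three labels correct, and nothing in Appendix 5 requests it.

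**The vector in the comment.** With eye listed before treatment, the columns are study-control, study-high, study-low, fellow-control, fellow-high, fellow-low. The vector `1 0 0 -1 0 0` is study-control minus fellow-control, so it also returns control. High dose would need `0 1 0 0 -1 0`.

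**Corrected vectors.** `0 0 1 -1 0 0` for high, `0 0 0 0 1 -1` for low and `1 -1 0 0 0 0` for control return 10, 4 and 0, as they should.

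**Sign.** The comment associates 1 with the study eye and −1 with the fellow eye. If those are the stored values, −1 sorts first and `eye 1 -1` becomes fellow minus study, which reverses every sign. If they describe coefficients, the sign is as intended provided that the study eye sorts first.

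**Appendices 4 and 7.** Using the same assumed values as arm means:

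- Levels sorting control, high, low: the High vs Control row is control − low = 0 − 4 = −4 instead of +10; the Low vs Control row is high − low = 10 − 4 = +6 instead of +4.
- Levels sorting High, Low, Placebo: the rows give 10 − 0 = 10 and 4 − 0 = 4, both correct.

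The documents do not settle which applies. Taken literally, Appendix 7's filters define two levels, which do not fit a contrast with three coefficients.

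**The case against.** The appendices are headed as sample code, contain placeholders and unwritten steps, and tell the programmer to adapt them. The Section 10 text governs and is clear about which arms are compared. Appendix 5 also requests the eye-by-treatment least-squares means, which would show the swap to anyone who looked. All this lowers the chance that a wrong result is reported. It does not make the contrasts agree with the coding printed beside them.

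A second objection is that SAP 10.2 describes this model for the low- and high-dose groups only. With levels 1 and 2 alone, the high and low pairs would fall on the right arms. But the six-coefficient vectors, the control row and the explicit code for control show that the appendix was written for three arms. If two were meant, the appendix conflicts with the text and still needs correcting. SAP 10.2 also lists surgical group in this model, and the Appendix 5 MODEL statement omits it.

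A reader might infer that Appendices 4 and 7 have a proven ordering error that reverses sign and arm. The documents do not support that. The 0/1/2 coding is stated only in Appendix 5. Appendix 7 uses character values, and SAP 5.5 and the binary part of Appendix 4 call the comparator placebo. Labels High/Low/Placebo would make the existing contrasts correct, and rewriting them for 0/1/2 would then break them.

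**Conclusion.** The Appendix 5 error stands: under its stated coding and SAS default ordering, three of three labelled rows return a different arm from the one named, and so does the alternative vector in the comment. This rests on treatment being stored as stated, or with labels that sort control, high, low, and on no level-order option being added.

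For Appendices 4 and 7 the finding is missing or inconsistent coding, not a demonstrated wrong result.

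The reach is limited. Appendix 5 serves one supportive analysis; Appendix 4 serves a COVID-19 sensitivity analysis and Appendix 7 a missing-data one. A reader might infer that the trial's main conclusions are exposed. They are not: the primary Fisher's exact test, the key secondary ANCOVA and the hierarchical testing do not use this code, and no alpha, power or sample-size figure depends on it. It should still be corrected before the code is used.

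**What to change.** 1. **Appendix 5.** Keep the 0/1/2 coding and put in the corrected vectors shown in the check, including the one for the reversed CLASS order in the comment. Alternatively, recode treatment so that it sorts high, low, control and leave the contrasts alone, or request differences by level label.
2. **Eye levels.** State how eye is stored and which level sorts first, so that the difference is study minus fellow.
3. **Check.** Compare each contrast with the eye-by-treatment least-squares means before use.
4. **Appendices 4 and 7.** State one three-level treatment coding across all appendices, replace the two-value filters in Appendix 7 with it, and match the contrasts to it. The `LSMEANS TRT / PDIFF CL` output already requested there is a useful cross-check, but the Rubin's-rule step reads the ESTIMATE output, so the contrasts themselves must be right.
5. **Model.** While editing, reconcile Appendix 5 with SAP 10.2 on whether control is included and on the surgical-group term.

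The cost is a few lines of code and comments, with no change to data or design.

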14.6 Appendix 6: Mixed Model Repeated Measures – Sample SAS Code

14.7 Appendix 7: Multiple Imputation based on MNAR – Sample SAS Code

```
*** make the data monotone missing ***;
PROC MI DATA=dset OUT=dset1 NIMPUTE=100 SEED=1234;
BY TRT:
VAR BASELINE VISIT2 VISIT3 VISIT4 VISIT5 VISIT6;
MCMC chain=multiple impute=monotone;
RUN;
*** for control arm, use all available data to impute missing data ***;
PROC MI DATA=dset1(where=(TRT='Placebo')) out=dset2 nimpute=1 seed=1235;
BY IMPUTATION ;
VAR BASELINE VISIT2 VISIT3 VISIT4 VISIT5 VISIT6;
MONOTONE REG(VISIT2=BASELINE/details);
MONOTONE REG(VISIT3=BASELINE VISIT2/details);
MONOTONE REG(VISIT4=BASELINE VISIT2 VISIT3/details);
MONOTONE REG(VISIT5=BASELINE VISIT2 VISIT3 VISIT4/details);
MONOTONE REG(VISIT6=BASELINE VISIT2 VISIT3 VISIT4 VISIT5/details);
RUN;
*** for active arm, impute missing data on VISIT2 using control arm ***;
PROC MI DATA=dset1(where=((TRT='Active' and VISIT2=.) or (TRT='Placebo'
                                                                                 and
VISIT2>.))) out=dset3 nimpute=1 seed=1235;
BY IMPUTATION ;
VAR BASELINE VISIT2;
MONOTONE REG(VISIT2=BASELINE/details);
RUN;
*** for active arm, impute missing data on VISIT3 using control arm ***;
PROC MI DATA=dset3(where=((TRT='Active' and VISIT3=.) or (TRT='Placebo'
                                                                                 and
VISIT3>.))) out=dset4 nimpute=1 seed=1235;
BY IMPUTATION ;
VAR BASELINE VISIT2 VISIT3;
MONOTONE REG(VISIT3=BASELINE VISIT2/details);
RUN:
*** repeat the same method for each sequential visit in active arm ***;
*** set all data together ***;
*** DSETX is the subset of active subjects with missing on VISIT2 ***;
*** DSETY is the subset of active subjects without missing on VISIT2 ***;
Data dsetall;
Set dset2 dsetX dsetY;
RUN:
*** Analyze the data on the last timepoint by ANCOVA ***;
PROC MIXED data=dsetall;
BY IMPUTATION ;
CLASS TRT;
MODEL CHG=BASELINE TRT;
LSMEANS TRT / PDIFF CL;
ESTIMATE "High vs Control" TRT 1 0 -1;
ESTIMATE "Low vs Control" TRT 0 1 -1;
ODS OUTPUT LSMEANS=LSMEAN;
ODS OUTPUT ESTIMATES=LSEST;
RUN:
*** Use Rubin's Rule ***;
PROC MIANALYZE parms=lsest;
BY LABEL;
MODELEFFECTS ALLEST;
ODS OUTPUT PARAMETERESTIMATES=PARMS;
RUN:
```

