10.4.3 Multiple Imputation Based on Missing Not at Random

For the change from baseline in BCVA, the pattern-mixture model using a control-based multiple imputation method will be performed based on missing data not at random for the ITT population. The method described here is based on methodology described by Little and Yau (1996) and extended in Ratitch and O'Kelly (2011). It assumes that subjects who discontinue from the study would have the same evolution of the disease as those subjects on the control group who remained in the study. The assumption that efficacy profiles of dropouts after discontinuation are similar to those of untreated control subjects is considered conservative because this methodology tends to minimize the difference between treatment and control groups. If the results of this analysis are in line with the primary efficacy results, then it can be confidently concluded that the primary analysis results are robust.

Biogen / NightstaRx,	Ltd
BIIB111	

Using this method, missing data after discontinuation will be imputed based on control group data using multiple imputation methodology for all subjects (including treatment subjects).

The steps to implement this sensitivity analysis are as follows (See sample SAS code in Appendix 7):

- 1. 100 datasets will be generated where missing data at intermediate visit(s) will be imputed for each treatment group using non-missing data from all subjects within the treatment group by a Monte Carlo Markov Chain (MCMC) imputation model using the MCMC statement in the SAS PROC MI procedure. As a result, each dataset will only have missing ending data, or a monotone missing data pattern.
- 2. For each dataset from Step 1, missing ending data will be imputed based on information from the control group. As a result, 100 imputed complete datasets will be generated.
 - Missing data at the first post-baseline visit will be imputed by a regression imputation model using the SAS PROC MI procedure with the REGRESSION option in the MONOTONE statement.
 - The SAS PROC MI procedure will use data from all control subjects as well as treatment subjects with missing data at the visit (i.e., only those that need imputation at the visit). Because subjects from treatment groups without missing data at the visit are excluded from this step, they will not contribute to the estimation of the imputation model for the visit.

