 - The same process will be used for all other visits. Subjects whose missing data were imputed at previous visits will contribute to the imputation for the next visit.
 - The regression imputation model includes an intercept and the slopes of the measurements from all previous visits.
- 3. Analyze each imputed complete dataset.
- 4. Combine estimates from the results of each model.

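### The Appendix 7 sample code leaves nearly all treated dropouts unimputed, contrary to SAP 10.4.3, and the sample contrasts do not fit the stated treatment coding

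*SAP*

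**What the plan says.** SAP 10.4.3 describes the method. Missing values after discontinuation are imputed from control data for all subjects, treated subjects included. Step 1 fills intermediate gaps within arm. Step 2 works forward visit by visit, using all controls "as well as treatment subjects with missing data at the visit (i.e., only those that need imputation at the visit", and "The same process will be used for all other visits". The section refers to Appendix 7 for sample code. It calls the approach conservative because "this methodology tends to minimize the difference between treatment and control groups", and says that agreement with the main result supports a confident claim of robustness.

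In Appendix 7 the controls are completed in one step ("for control arm, use all available data to impute missing data", giving `dset2`). For the treated arms, `dset3` takes active subjects with VISIT2 missing. The next step reads that subset: "PROC MI DATA=dset3(where=((TRT='Active' and VISIT3=.) or". Later visits are covered by a comment to repeat the method. The final stack is `dset2`, `dsetX` and `dsetY`, where "DSETY is the subset of active subjects without missing on VISIT2".

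On coding, Appendix 5 states "treatment is coded as 1-high dose, 2-low dose, 0-control" and gives an alternative contrast, "ESTIMATE 'high dose:study eye vs fellow eye' eye 1 -1 eye*trt 1 0 0 -1 0 0". Appendices 4 and 7 use `TRT 1 0 -1` for high versus control and `TRT 0 1 -1` for low versus control. None of these models shows an `ORDER=` option.

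**The concern.** The text of 10.4.3 is sound, but the code it points to selects different subjects. A treated subject with VISIT2 observed who drops out later enters no imputation step, and PROC MIXED discards him because his change score is missing. Control dropouts are kept. The comparison becomes treated completers against all controls.

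That removes the feature that makes the analysis conservative, namely giving treated dropouts a control-like course. If subjects with poor outcomes leave, deleting them raises the treated mean. The analysis meant to stress the LOCF result would then tend to look better than it.

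The second matter is that contrast coefficients in SAS follow the sorted class levels. If the levels do not sort as high, low, control, the output labels name the wrong arms.

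**Working it through.** The SAP gives no figure to reproduce here. The check is a trace of the code, a simulation for size, and a mapping of the contrasts.

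**1. Trace of Appendix 7 for a treated subject.** The pattern is monotone after step 1, with five post-baseline variables VISIT2 to VISIT6.

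| Post-baseline visits observed | In `dset3` | In `dset4` | Final-visit value |
|---|---|---|---|
| 0 | yes | yes | imputed |
| 1, 2, 3 or 4 | no | no | missing, dropped by PROC MIXED |
| 5 | no | no | observed |

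**2. Who is affected.** ITT (SAP 7.3) requires at least one post-treatment BCVA. Controls have only telephone contacts at Visits 2 to 4 (Protocol Table 3), so their scheduled BCVA starts at Month 1 and a control-based regression can only start there. If VISIT2 means Month 1, the only treated ITT subjects missing it after step 1 are those with BCVA at Day 1 or Day 7 (or an unscheduled visit) alone. All other treated dropouts are left unimputed. With 64 + 32 = 96 treated and 5, 10 or 20% dropout, that is 4.8, 9.6 or 19.2, or about 5, 10 or 19 subjects.

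**3. Size.** The documents give no dropout rate, BCVA SD or dropout mechanism. Assumed: gain 5 letters, SD of change 9, correlation 0.7, visits at Months 1, 4, 8 and 12, and equal dropout in all arms. From the documents: arms of 64/32/64, and a control decline of 0.5 letters per 20 months (SAP 5.5). Dropout weight is exp(−s·z), with z the standardised Month 1 change. There were 600 replicates with 20 imputations using Bayesian regression draws; the Monte Carlo SE of the differences is at most 0.02.

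High dose versus control, code as written minus text method, in letters:

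| Dropout mechanism | 5% | 10% | 20% |
|---|---|---|---|
| Random (s = 0) | +0.05 | +0.12 | +0.17 |
| Mild (s = 0.5) | +0.23 | +0.42 | +0.87 |
| Moderate (s = 1.0) | +0.36 | +0.72 | +1.42 |
| Moderate, a quarter of treated dropouts with Day 1/7 BCVA only | +0.25 | +0.49 | +1.02 |
| Strong (s = 1.5) | +0.46 | +0.92 | +1.73 |

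The moderate estimates behind these are 5.25 against 4.89, 5.62 against 4.90, and 6.20 against 4.79 (the last difference is 1.42 before rounding). At 10% moderate dropout the code exceeds the LOCF estimate in 91% of simulated trials, and the text method does so in 33%. At 10% and s = 1.5 (300 replicates), varying the gain from 2 to 8, the SD from 7 to 12 and the correlation from 0.5 to 0.85 gives +0.72 to +1.16.

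A repeat of the moderate case with 250 replicates and 10 imputations gave +0.36, +0.68 and +1.43, with 88% against 33% for the LOCF comparison. A separate random-dropout run gave 5.06, 5.03 and 4.84 for the code and 5.02, 4.94 and 4.73 for the text, so differences of 0.04, 0.09 and 0.11.

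**4. Contrasts under 0 = control, 1 = high, 2 = low, sorted ascending.**

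| Label | Coefficients | What is estimated |
|---|---|---|
| High vs Control (Appendices 4, 7) | 1 0 −1 | control − low |
| Low vs Control (Appendices 4, 7) | 0 1 −1 | high − low |
| Appendix 5, high dose | 1 −1 0 0 0 0 | eye contrast in control |
| Appendix 5, low dose | 0 0 1 −1 0 0 | eye contrast in high dose |
| Appendix 5, control | 0 0 0 0 1 −1 | eye contrast in low dose |
| Appendix 5, alternative class order, high dose | 1 0 0 −1 0 0 | eye contrast in control |

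The Appendix 5 rows assume control subjects are in the dataset, which the third contrast needs. If eye is stored as −1/1, the fellow eye sorts first and the sign also reverses. SAP 10.2 names only the two dose groups for this model. Without control rows the first two labels would be right and the third would have no arm. In Appendices 4 and 7, labels that sort as High, Low, Placebo make both contrasts correct. Sorting 0/1/2 in descending order gives low − control and high − control, so the labels are swapped.

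**The case against.** The strongest reply is that the governing text is right and Appendix 7 is only a template. It cannot run as printed: it filters on Active and Placebo in a three-arm trial, never builds `dsetX` or `dsetY`, and does not define VISIT2 to VISIT6. Protocol Visit 2 is Day 0, with no scheduled BCVA. A programmer must rewrite it with 10.4.3 as the specification. That is true and limits the point, since the harm arises only if the selection rule is carried over. But the rule is not a gap left to be filled. The shown link from `dset3` to the next step and the split by VISIT2 both apply it, and repeating the same method continues it. The resulting deletion raises no error.

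On the contrasts, the 0/1/2 coding is stated only in Appendix 5. SAP 5.5 and Appendix 4 speak of placebo, and labels High, Low, Placebo would sort correctly. Appendix 5 also warns that variable order matters. This stands: the Appendix 4 and 7 mismatch is conditional on coding, and the Appendix 5 mismatch on default order and on control rows being present.

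The sizes are driven by assumptions. At s = 1.0 a subject 1 SD below the mean is e² = 7.4 times as likely to drop out as one 1 SD above. Under random dropout the shift is small. That stands too.

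Finally, only a sensitivity analysis of a key secondary endpoint is at stake, and the MMRM remains as another check. That argues for modest weight, but the SAP relies on this analysis for its robustness claim.

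**Conclusion.** The concern holds. Read as written, Appendix 7 does not implement 10.4.3: later treated dropouts are deleted and control dropouts are imputed. This reaches nearly all treated dropouts if VISIT2 is the first modelled post-baseline visit. Across 5 to 20% assumed dropout, the upward shift in the high-dose effect is about 0.05 to 0.17 letters if dropout is random and 0.36 to 1.42 letters if it depends moderately on poor outcome. These figures illustrate size; they do not predict the trial's result.

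The contrast point is secondary and conditional on the coding, sort order and dataset used.

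The scope is one sensitivity analysis of the first key secondary endpoint, the supportive fellow-eye model, and the continuous-endpoint contrasts in the COVID-19 missing-at-random sensitivity analysis. The primary Fisher test with missing counted as failure, the LOCF ANCOVA and the MMRM are not touched. It should be corrected, but it does not threaten the primary conclusion.

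**What to change.** **Appendix 7.** At each visit, take every treated subject still missing at that visit from the full running dataset, including those observed earlier, add the controls, and carry imputed values forward. Alternatively, use PROC MI with `CLASS TRT`, `MONOTONE REG` and an `MNAR MODEL(... / MODELOBS=(TRT='Placebo'))` statement, with arm labels matched to the data. Define VISIT2 to VISIT6. Add a check that every ITT subject has a Month 12 value in all 100 datasets.

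**Appendices 4, 5 and 7.** Use one three-level treatment coding and state the level order, or write contrasts that name the levels. For 0/1/2 in ascending order, the coefficients are −1 1 0 for high versus control and −1 0 1 for low versus control. In Appendix 5, state how eye is stored and whether control rows are included.

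**Minor alignment.** Add surgical group to the sample models. SAP 5.5 and 10.2 require it for Appendices 4 and 5, and the main ANCOVA implies it for Appendix 7.

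The cost is an edit to sample code before database lock, with no new data and no change to the planned method.
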